1 INTRODUCTION

1.1 Background

This clinical study provides a preliminary evaluation of Navidea's radiopharmaceutical Tc 99m tilmanocept as an imaging agent for the detection of CD206 (Cluster of Differentiation 206, the macrophage mannose receptor) expressing macrophages in the liver as a possible indicator of pathological processes related to nonalcoholic steatohepatitis (NASH). NASH is a chronic inflammatory disorder. Tc 99m tilmanocept contains mannose groups attached to a dextran backbone, enabling Tc 99m tilmanocept to bind strongly to CD206 expressed on the surface of several classes of activated macrophages. Elevated levels of activated macrophages are associated with liver inflammation raising the possibility that imaging Tc 99m tilmanocept localizations by single-photon emission computed tomography (SPECT) could be used alone or in combination with other diagnostic tests to identify persons with NASH.

NASH is an emerging public health concern affecting millions of persons. There is an urgent unmet need to develop noninvasive methods to augment and improve the accuracy of diagnostic evaluations of patients suspected of having NASH. Currently, liver biopsies in combination with various clinical findings are the most accurate means for diagnosing NASH [2]. However, such procedures are invasive and potentially challenging to deliver to a patient population as large as the one comprised of those suspected of having NASH. The primary objective of this study is to determine diagnostic feasibility and to explore a variety of imaging protocol parameters to provide a preliminary determination of an optimized imaging protocol for Tc 99m tilmanocept in NASH patients. Developing a non-invasive NASH diagnostic would greatly facilitate the delivery of new NASH therapeutics, many of which are currently in clinical trials [3-6].

Nonalcoholic fatty liver disease (NAFLD) is characterized by an accumulation of the fat in the liver cells. Histological evaluation of a liver biopsy revealing accumulation of fat without inflammation and associated damage is diagnosed as NAFLD. NAFLD is considered to be a hepatic manifestation of metabolic syndrome and develops in patients with non-significant alcohol usage. NAFLD progression leads to further accumulation of fat in the hepatocytes, inflammation, and damage to liver cells that is diagnosed NASH (see Figure 1). NASH is a silent disease. Further progression of NASH leads to NASH-associated liver fibrosis, cirrhosis and hepatocellular carcinoma. These NASH derived pathologies are the fastest growing indications for liver transplantation, while at the same time liver transplantation shortage is a major issue [8-10].

[figure not shown]

Figure 1. Nonalcoholic steatohepatitis (NASH) progression [7]

Changing diets and activity levels are causing a growing global obesity epidemic with the result that metabolic syndrome and its associated NAFLD are becoming more prevalent. Many of these individuals with NAFLD are progressing to NASH, exasperating the growing need for better and more assessable means to diagnose and manage this emerging patient population. Recent analysis of this epidemic showed global prevalence of NAFLD to be approximately 25% - 37% with the highest risk in the Middle East, South America and lowest in Africa [11, 12]. It is estimated that 30% of the US population has developed NAFLD with the prevalence of NASH currently at 5.7% [12]. Moreover, in 2010, 417,524 patients had NASH-associated cirrhosis, and 4,104,871 had NASH-associated advanced fibrosis based on National Health and Nutrition Examination Survey (NHANES) data [13].

NASH is an inflammatory syndrome in which immune cells infiltrate into and accumulate in liver tissue [14, 15]. Numerous among these immune cells are macrophages. There are two types of macrophages in the liver. The first type consists of Kupffer cells (aka stellate macrophages) that reside within the endothelial lining of blood vessels in the liver. The second type of macrophages in the liver consists of macrophages differentiated from bone marrow derived monocytes that have infiltrated into the liver and developed into activated macrophages in response to inflammatory signals originating in the liver [14]. It is hypothesized that Tc 99m tilmanocept, through its affinity to CD206, will bind to and accumulate in both types of liver macrophages permitting the degree and anatomical distribution of Tc 99m tilmanocept localization to be used as an indicator of the presence and intensity of NASH related hepatic inflammation. In addition, NASH results in the development of fibrotic lesions in the liver, basically scars resulting from resolved inflammation. These fibrotic lesions are depleted of macrophages, thus are expected to be regions of much reduced Tc 99m tilmanocept localization relative to regions where NASH related inflammation is ongoing [1, 16, 17]. In both cases of either increased Tc 99m tilmanocept localization due to active NASH mediated inflammation or decreased Tc 99m tilmanocept localization due to macrophage depletion due to fibrotic resolution of NASH mediated inflammation, the degree and distribution of Tc 99m tilmanocept localization is expected to significantly differ in NASH involved livers relative to the degree and distribution of Tc 99m tilmanocept localization

observed in livers which are not involved in NASH inflammation. This clinical study will provide a preliminary evaluation of the degree and distribution of Tc 99m tilmanocept localization in healthy livers and those involved in NASH inflammation. If this and follow on studies are successful in establishing that Tc 99m tilmanocept enabled imaging can identify areas of NASH involvement or resolution, then it may be possible to develop Tc 99m tilmanocept as a NASH imaging agent that can assist physicians to non-invasively diagnose and monitor NASH, thus satisfying the need for a non-invasive means to diagnose and assess NASH.

1.2 Liver Anatomy, Function, and Role of Kupffer cells

The liver is the largest internal organ, responsible for filtration of the blood coming from a digestive tract before passing it to the rest of the body (Figure 2) [19]. Liver is made up of microscopic lobules, including acinus. Acinus is constructed of interconnected hexagonal units packed with spokes-like internal canals transporting blood and bile ducts across tightly packed hepatocytes. Each acinus unit has three functional zones [20, 21]. Zone 1 (periportal) performs a majority of metabolic functions and contains the most oxygenated blood. Zone 2 (midzone) is situated between zones 1 and 3. Zone 3 (centrilobular) borders the central vein although it has the poorest oxygenation, and is the most susceptible to a restriction in blood supply to tissues resulting in ischemic damage, abnormal retention of lipids within the cell (steatosis), hepatocellular ballooning and hepatocyte death resulting in scar tissues (fibrosis) leading to possible progression to cirrhosis. Zone 3 is the anatomical location where NASH pathology and its consequences are most pronounced. In addition, activated Kupffer cells produce TGFB and other cytokines that promote liver fibrosis [22]. Interestingly, during the process of liver inflammation and hepatocyte injury (ballooning), Kupffer cells have an ability to differentiate into activated macrophages, many of which highly express CD206 (see Figure 3) [23]. This observation further supports the hypothesis that Tc 99m tilmanocept binding to CD206 can facilitate imaging of NASH associated inflammation.

Confidential Page 21 of 71

[figure not shown]

Figure 2. Liver anatomy and lobular zoning [18]

1.3 NASH Diagnosis and Other Imaging Modalities

Since NASH manifests as a chronic and gradually progressive inflammatory syndrome of the liver and since NASH-related liver inflammation is associated with large numbers of liver infiltrating CD206 expressing activated macrophages, Tc 99m tilmanocept enabled imaging of NASH inflamed livers could facilitate a diagnosis of NASH through observation of Tc 99m tilmanocept localization to areas of CD206-expressing macrophage aggregations associated with NASH inflammation.

Today, physicians use a variety of imaging modalities to inform a diagnosis of NASH [24-26]. These alternatives to Tc 99m tilmanocept based imaging for NASH include ultrasound (US), computerized tomography (CT), magnetic resonance spectroscopy (MRS) and magnetic resonance imaging (MRI). All of these imaging modalities have their pros and cons, but most

importantly and unlike Tc 99m tilmanocept, none of these other imaging modalities directly image inflammatory processes [25]. Instead they measure either liver fat deposition or evidence of liver fibrosis [16, 24, 27]. NASH, especially in its earlier stages and before extensive tissue damage has occurred and when one would most likely want to initiate therapy, may not be associated with significant fibrosis. Thus, evaluating livers only for fibrosis introduces a diagnostic sensitivity issue into the diagnostic work up of patients suspected of having NASH. Conversely, evaluating a patient's liver for fat content can introduce a diagnostic specificity issue related to discriminating between NAFLD and NASH. Since, NAFLD is a very common condition with limited clinical consequences, confusing NAFLD and NASH is problematic. By contrast, Tc 99m tilmanocept may be capable of imaging NASH inflammation directly. As inflammation is central to the pathology of NASH [24], Tc 99m tilmanocept may localize conspicuously and specifically in the livers of patients with NASH.

In addition to the imaging modalities discussed in the previous paragraph, many investigators have evaluated the utility of using various ^{99m}technetium colloids as imaging liver agents [1, 16, 17, 27]. In fact, Tc 99m sulfur colloid will be evaluated as a comparator to Tc 99m tilmanocept for liver imaging in this protocol. Colloids are particles that are actively phagocytized by Kupffer cells. When injected into the blood circulation, Tc 99m sulfur colloid is rapidly cleared from the circulation by the Kupffer cells [26]. Tc 99m sulfur colloid localization to Kupffer cells enables SPECT imaging of livers. Tc 99m tilmanocept localization is expected to differ from Tc 99m sulfur colloid localization in two ways. First, colloidal particles are expected to penetrate poorly into the liver. Thus, Tc 99m sulfur colloid will be unable to localize to aggregates of activated macrophages that have penetrated into liver tissue. Second, Tc 99m sulfur colloid localization to Kupffer cells is independent of their cellular activation state and CD206 expression phenotype. Conversely, Tc 99m tilmanocept localization is CD206 dependent and the extent of localization is expected to vary relative to the level of CD206 expression and the density of CD206 expressing cells.

[figure not shown]

Figure 3. Involvement of the macrophages in the liver damage [15]

Abbreviations: CCL2, CC-chemokine ligand 2; CCR2, CC-chemokine receptor 2; CSF1, macrophage colony-stimulating factor 1; CSF1R, CSF1 receptor; CX3CR1, CX3C-chemokine receptor 1; CXCR, CXC-chemokine receptor; CXCL, CXC-chemokine ligand; DAMPs, damage-associated molecular patterns; FASL, FAS ligand; IL-1β, interleukin-1β; IL-6, interleukin-6; IL-10, interleukin-10; LSEC, liver sinusoidal endothelial cell; LY6C, lymphocyte antigen 6 complex; MoMFs, monocyte-derived macrophages; MSR1, macrophage scavenger receptor 1; NO, nitric oxide; PGE2, prostaglandin E2; ROS, reactive oxygen species; TNF, tumour necrosis factor; VEGFA, vascular endothelial growth factor A.

1.4 Preliminary Data

1.4.1 ^{99m}Tc-tilmanocept (Lymphoseek®)

Tc 99m tilmanocept is a radiopharmaceutical imaging agent that was originally designed to bind specifically and with high affinity to CD206 on macrophages that reside in lymph nodes (Figure 4). Tilmanocept is a macromolecule consisting of multiple units of DTPA (diethylenetriaminepentaacetic acid) and mannose, each synthetically attached to a 10 kDa dextran backbone via amine terminated molecular leashes. The mannose acts as a ligand for CD206 while the DTPA moieties serve as chelating agents for labeling with ^{99m}technetium (^{99m}Tc).

Tc 99m tilmanocept Clinical Study Protocol Number: NAV3-30

Figure 4. Structure of Tc99m-tilmanocept (Lymphoseek®)

Showing attachment of multiple units of DTPA and mannose to a backbone of dextran. The chelating agent, DTPA, is shown holding an atom of 99mTechnetium.

The final construct has an average molecular weight of 18.7 kDa, is highly water soluble and has an apparent particle diameter of 7 nm. Tilmanocept's multiple mannose moieties permit it to bind multivalently with very high affinity ($K_D = 2.7 \times 10^{-11} M$) to CD206 through CD206's 8 mannose binding domains. Multivalent binding is required for this high affinity interaction [28]. After binding to CD206, tilmanocept is internalized and accumulates in endosomes. Tilmanocept is protected by the U.S. patent #6,409,990.

Following various preclinical studies in both cells based assay systems and in various animal species and following numerous clinical studies (including three phase 3 trials) in human subjects with breast cancers, melanomas, and head and neck cancers [29-34], Lymphoseek® was approved by the United States Food and Drug Administration (FDA) in 2013 [35] for use as a lymphatic mapping agent in patients undergoing surgeries to remove melanomas and breast tumors without presurgical evidence of metastatic disease. Since then, the indications for which Lymphoseek® has been approved have been expanded to all lymphatic mapping to assist in the localization of lymph nodes draining a primary tumor site in patients with solid tumors for which this procedure is a component of intraoperative management and for guiding sentinel lymph node biopsy (SLNB). Additionally, Lymphoseek® is approved in the European Union (EU) for use in imaging and intraoperative detection of sentinel lymph nodes (SLNs) draining a primary tumor in adult patients with breast cancer, melanoma, or localized squamous cell carcinoma of the oral cavity. Lymphoseek® has an extraordinary safety record. Since its first regulatory approval in 2013, Lymphoseek® has been injected into over 170,000 cancer patients for various SLN related indications. To date, there have been no serious adverse events associated with these procedures that have been attributed to Lymphoseek[®]. Typical of how Lymphoseek® is used, Figure 5 shows a SPECT/CT image of a breast cancer patient injected peritumorally with Lymphoseek[®]. Localization to a SLN is clearly shown.

[figure not shown]

Figure 5. Pre-operative SPECT-CT image of a breast cancer patient who had been injected peritumorally with ^{99m}Tc-tilmanocept

Lymphatic transport and accumulation in the first encountered lymph node, the sentinel lymph node (SLN), is observed.

1.4.2 Transitioning from Subcutaneous and Intradermal Administration of ^{99m}Tc-Tilmanocept to IV Administration in Diagnostic Imaging indications

For all previously approved SLN and lymphatic mapping indications, the approved routes of administration were subcutaneous, intradermal or peritumoral injection. Intravenous (IV) injection, as is proposed in this protocol has not been approved as part of the label for Lymphoseek[®]. It is well known that CD206 expressing macrophages aggregate at sites of inflammation associated with a number of serious illnesses. Navidea wishes to expand the approved diagnostic indications for which ^{99m}Tc-Tilmanocept is approved to include several new diagnostic imaging indications that exploit the pathological aggregations of CD206 expressing macrophages associated with these illnesses. Most if not all of these alternative indications, including the one proposed in this protocol for imaging NASH inflammation, will require IV administration.

1.4.3 Nonclinical Evaluations – IV Administration

Dosing In Rats: In preparation to initiate the IV route of administration, eleven (11) preclinical tests were conducted to assess safety, toxicity, and interaction potential at doses hundreds to thousands of times the expected maximum human dose, as summarized below:

Type of Study / Description	Test System	Method of Administration	Dosing
Central nervous system safety pharmacology	Rat	Intravenous	37, 190, and 380 μg/animal or equivalent 490X and 61X the anticipated study doses of 50 μg and 400 μg in humans

Clinical Study Protocol Number: NAV3-30

Type of Study / Description	Test System	Method of Administration	Dosing
Expanded single-dose toxicology (including toxicokinetics and local tolerance)	Rat	Intravenous	37, 190, and 380 μg/animal or equivalent 490X and 61X the anticipated study doses of 50 μg and 400 μg in humans
Respiratory Safety Pharmacology Evaluation Using Head- Out Plethysmography of Tilmanocept following Intravenous Bolus Injection in Male Rats	Rat	Intravenous	60, 120, and 300 μg/animal or equivalent 320X and 41X the anticipated study doses of 50 μg and 400 μg in humans
In Vitro Evaluation of Tilmanocept as an Inhibitor of Cytochrome P450 (CYP) Enzymes in Human Liver Microsomes	Human Liver Samples	In vitro	0.6 to 600 nM
In Vitro Evaluation of Tilmanocept as an Inhibitor of Human ABC and SLC Transporters	Human Liver Samples	In vitro	0.04, 0.4 μΜ
Pharmacokinetics, Excretion, and Distribution by Quantitative Whole- Body Autoradiography Following Intravenous Administration of 99mTc-Tilmanocept in	Rat	Intravenous	25 μg in 0.5 mL with collection of Blood, Urine, Feces, and Carcasses for QWBA
Rats Hemolysis and protein flocculation	Human blood samples	In vitro	2.5, 25, and 250 μg/mL whole human blood
Target profiling screen	Ion Channel	In vitro	See Individual Tests Below

Confidential

Type of Study /		Method of	Dosing
Description	Test System	Administration	_
K Ion Channel	Ion Channel	The cardiac potassium channel, hERG, is responsible for a rapid delayed rectifier current (IKr) in human ventricles. This channel has been selected for evaluation because inhibition of IKr is the most common cause of cardiac action potential prolongation by noncardiac drugs. In this assay, hERG potassium channels are expressed in a human embryonic kidney (HEK293) cell line that lacks endogenous IKr.	0.025, 0.05, 0.25, 0.5 mg/mL
Na Ion Channel	Ion Channel	Cloned hNav1.5 sodium channels (SCN5A gene expressed in CHO cells)	0.025, 0.05, 0.25, 0.5 mg/mL
Ca Ion Channel	Ion Channel	1. Cloned L-type calcium channels (hCav1.2, encoded by the human CACNA1C gene and coexpressed with the β2 subunit, encoded by the human CACNB2 gene and the α2δ1 subunit encoded by the human CACNB2 gene in CHO cells), responsible for ICa,L, high threshold calcium current. 2. Cloned hNav1.5 sodium channels (SCN5A gene expressed in CHO cells).	0.025-0.5 mg/mL

Conclusions from These Tests:

CNS: In conclusion, a single IV administration of tilmanocept was well tolerated in rats at levels of 0.15, 0.75, and 1.50 mg/kg. Brief sedation shortly after dosing was observed at 0.75 and 1.50 mg/kg, which resolved by the time of the first functional observational battery assessments and was attributed to the mannosyl-dextran content of tilmanocept. There were no tilmanocept-related effects on functional observational battery parameters.

Single Bolus Toxicity: Tilmanocept-related clinical pathology changes were limited to minimally greater, dose-related, aspartate aminotransferase (AST) values for 0.75 and 1.5 mg/kg males and females that were likely caused by muscle or erythrocyte release as changes did not occur in other hepatobiliary-related clinical pathology parameters. This change had resolved at the end of the recovery phase.

At the Day 2 necropsy, dark focus in the glandular stomach was considered to be a potential test article-related gross pathology finding in males at ≥ 0.75 mg/kg. The gross finding of dark focus in the stomach correlated microscopically with focal erosion or minimal hemorrhage. Focal erosion in the stomach was test article related in males at ≥ 0.75 mg/kg, but was considered to be of little toxicological significance. No test article-related organ weight changes were noted. At the end of the recovery phase (Day 15), there were no test article-related findings in gross pathology, organ weights, or histopathology.

Respiratory: In conclusion, respiratory function was assessed in male Crl:CD(SD) rats given a single intravenous injection dose of vehicle control article or 0.150, 0.300, or 0.750 mg/kg of tilmanocept at a dose volume of 3 mL/kg. Administration of tilmanocept had no effect on mortality, but it was associated with severe abnormal clinical observations of hypoactivity, ataxia, labored or irregular respiration, and pale skin of entire body for animals given 0.750 mg/kg. Administration of >0.150 mg/kg tilmanocept had no direct effect on respiration rate, but it was associated with higher tidal volume (up to +26, +14, and +50% in animals given 0.150, 0.300, or 0.750 mg/kg, respectively) and higher minute volume (up to +18, +5, and +40% 0.5 through 1 hour post-dose in animals given 0.150, 0.300, or 0.750 mg/kg, respectively).

CYP: This study was designed to independently evaluate the in vitro inhibitory effect of tilmanocept on major CYP enzymes in human liver microsomes. Specifically, the inhibition of CYP1A2, CYP2B6, CYP2C8, CYP2C9, CYP2C19, CYP2D6 and CYP3A4/5 (utilizing two different substrates) by tilmanocept was assessed with the aim of ascertaining the potential of tilmanocept to inhibit the metabolism of concomitantly administered drugs.

To evaluate tilmanocept as a direct, time-dependent and metabolism-dependent inhibitor of CYP activity, human liver microsomes from a pool of 200 human donor sources were incubated with marker substrates in the presence or absence of tilmanocept. To distinguish between timedependent and metabolism-dependent inhibition, tilmanocept was preincubated with human liver microsomes for 30 min without and with an NADPH-generating system, respectively, prior to the incubation with the marker substrate. Known direct and metabolism-dependent inhibitors of CYP enzymes were included as positive controls in all experiments.

Under these experimental conditions, there was little or no evidence of direct, time- or metabolismdependent inhibition of any CYP enzyme by tilmanocept.

ABC and SLC transporters: It was found that tilmanocept was not an inhibitor of human transporters (namely P-gp, BRCP, OAT1B1, OATP1B3, OAT1, OAT3, and OCT2) under the conditions tested.

Drug Distribution: Drug-related radioactivity was widely distributed throughout the whole body. The highest mean concentrations of radioactivity were observed in urine > kidney cortex > liver > kidney > kidney medulla > bile > spleen > spleen red pulp > spleen white pulp > urinary bladder between 0.25 and 36 hours post-dose. The concentration of radioactivity in other tissues was low (<500 ng equivalents 99mTc-Tilmanocept/g) and maximum levels were generally observed between 0.25 and 2 hours post-dose. Concentrations declined over time and were not detectable in the majority of the tissue by 36 hours post-dose. The exceptions were the kidney, liver, spleen, and urine, in which concentrations were still detectable at 48 hours post-dose. By 72 hours post-dose levels of radioactivity in all tissues were not detectable.

The main route of elimination of drug-related radioactivity following an IV administration of 99mTc-Tilmanocept was via urine, with a mean 38.9% of the dose administered detected in urine over 0 to 120 hours post-dose. A mean of 10.0% of the administered dose was eliminated via feces. The total recoveries were a mean of $50.8 \pm 4.87\%$ over the measurable time period for technetium Tc99m detection (t0.5 = 6.02 hr).

Hemolysis: No hemolysis and no flocculation were observed following in vitro treatment of human whole blood with tilmanocept at final whole blood concentrations of 2.5, 25 or 250 μ g/mL.

Ion Channels (Na+, K+, Ca2+): Although there is a small dose-dependent effect that is fractional to the positive control, variability within concentration renders the median value observations not significantly different (Kruskal-Wallis).

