7.2.3.3 After Administration of Tc 99m Tilmanocept

The following procedures will be completed at the specified times:

- 20 ± 5 Minutes After Administration:
 - Assessment of AEs
 - o ECG (completed before vital signs)
 - Vital signs after at least 1 minute in a resting position (body temperature, heart rate, blood pressure, and respiratory rate)
 - o Planar imaging of the liver/spleen followed by SPECT/CT of the liver/spleen and abdomen
- 75 ± 15 Minutes After Administration:
 - Assessment of AEs

Confidential

Clinical Study Protocol Number: NAV3-30

- o Planar imaging of the liver/spleen followed by SPECT/CT of the liver/spleen and abdomen
- 180 ± 15 Minutes After Administration:
 - Assessment of AEs
 - o Planar imaging of the liver/spleen followed by SPECT/CT of the liver/spleen and abdomen
- After Completion of All Imaging:
 - o Blood draw for hematology and chemistry testing
 - o Urine collection for urinalysis

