8.2 SPECT/SPECT-CT Image Acquisition

The camera used to obtain the images should be a dual-headed SPECT or SPECT/CT camera equipped with a low-energy, high-resolution collimator with a 15% window (20% can be used if 15% setting not available) centered over a 140keV peak.

The camera must have passed the daily SPECT QC tests as per the manufacturer's recommendation for that day's scan schedule.

Whenever possible, subjects should be asked to void after injection and prior to the first imaging session and again between imaging sessions.

Subjects should be positioned supine with arms at their side. The subject's head, legs, hands, and hips should be in the true anterior position. The subject should be instructed to remain as motionless as possible during the scan, and asked to breathe as shallowly as comfortable when the camera is passing over the chest. To help minimize leg motion, a light taping around the ankles can be used to keep the legs together. A pillow under the knees is often very helpful for comfort.

A planar scan of the liver followed by SPECT/CT should be obtained at the following time points following administration of the specified product:

Unfiltered Tc 99m Sulfur Colloid:

• 20 ± 5 minutes post administration

Tc 99m Tilmanocept:

- 20 ± 5 minutes post administration
- 75 ± 15 minutes post administration
- 180 ± 15 minutes post administration

It is anticipated that the planar scan would be acquired for 25-30 minutes. Using state-of-the-art 2-headed cameras (nominal 20" x 15" FOV), a target of 5-7 million counts should be obtained for the summed view of both heads. For higher activity injections, it may be possible to attain this target in a shorter time, allowing the subject more time off the bed between scans. A simple measure of the subject's "thickness" (i.e. from a lateral visual view, the height of the subject's anterior-most chest/abdomen above the scan bed) should be documented. This will be used for the attenuation correction to be applied to the anterior/posterior views obtained from the planar scan.

Following completion of the planar imaging session at the designated time points, a 3D SPECT/CT should be obtained on the liver, spleen, and abdomen, followed by a patient break.

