9.3 Efficacy Variables

The efficacy variables for this study are as follows:

- Liver uptake of unfiltered Tc99m-labeled sulfur colloid and tilmanocept; and,
- Intrahepatic distribution (tessellation) of Tc99m-labeled sulfur colloid and tilmanocept

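### Absolute liver intensity is compared between NASH and control subjects with no normalisation to injected activity and no within-scan reference, so it is confounded with delivered activity

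*Combined protocol and SAP*

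**What the plan says.** Section 9.3 lists two efficacy variables, "Liver uptake of unfiltered Tc99m-labeled sulfur colloid and tilmanocept" and "Intrahepatic distribution (tessellation) of Tc99m-labeled sulfur colloid and tilmanocept". Neither has a unit, a denominator or a reference region. Section 9.5.3 builds non-parametric densities from voxel intensities for each agent, per subject and then pooled by NASH or control. That sentence does not mention radiolabel level. The synopsis splits localization rates by tilmanocept dose group, but its sentence on intensities mentions only time point and comparison with controls.

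Section 5.2 fixes the tilmanocept mass at 200 µg and allows the administered mass and activity to fall within 20% of assignment. The first two NASH subjects receive 8.0 mCi. The first review may then send three further NASH subjects and three controls to 2.5 mCi (option 1), or continue at 8.0 mCi with a possible later 2.5 mCi stage (option 2). Section 5.5 asks for a record of product dispensed. It does not mention residual syringe activity or net injected activity.

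The spleen is in the field at the Day 0 session (section 7.2.2.3) and at all three Day 3 sessions, where section 7.2.3.3 specifies "Planar imaging of the liver/spleen followed by SPECT/CT of the liver/spleen and abdomen". Section 8.2 repeats that "a 3D SPECT/CT should be obtained on the liver, spleen, and abdomen, followed by a patient break". No planned output uses it. The evidence for splenic uptake of intravenous tilmanocept is a rat study (section 1.4.3, "with collection of Blood, Urine, Feces, and Carcasses for QWBA"), which reports of tissue clearance: "The exceptions were the kidney, liver, spleen, and urine, in which concentrations were still detectable at 48 hours post-dose".

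**The concern.** Section 1.1 expects fibrotic regions to show much reduced tilmanocept localization, and section 4.1.1 restricts NASH subjects to fibrosis stage F3-F4. Lower hepatic signal is therefore one of the disease effects the study looks for. Lower delivered activity produces the same change in absolute intensity. With three to six subjects per group, a reader of the pooled densities could take a dose difference for a disease difference, or miss a real one that dose has masked. The problem concerns absolute uptake and intensity. A factor common to every voxel of a scan leaves the relative intrahepatic pattern as it was.

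**Working it through.** The plan's only statistical figure is N=12. Section 9.4 gives no alpha, power, effect or SD, so no formula reproduces it. It equals the largest head count that section 5.2 allows: 2 + 1 + 3 + 3 + 3 = 12 (option 2 in full). Option 1 gives 2 + 3 + 3 = 8, and option 2 stopped at the second review gives 2 + 1 + 3 = 6.

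**Size of the confounding (inputs from section 5.2; half-life 6.02 h from the abbreviations list)**

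1. Within one radiolabel level, extremes of tolerance: 1.2 / 0.8 = 1.5-fold.
2. Between nominal levels: 8.0 / 2.5 = 3.2-fold; at opposite tolerance limits, (8.0 × 1.2) / (2.5 × 0.8) = 9.6 / 2.0 = 4.8-fold.
3. Option 1, all NASH subjects pooled: mean (2 × 8.0 + 3 × 2.5) / 5 = 23.5 / 5 = 4.7 mCi, against 2.5 mCi in controls; 4.7 / 2.5 = 1.88-fold from dose alone.
4. Option 2 in full: each group has three subjects at each level, mean (3 × 8.0 + 3 × 2.5) / 6 = 5.25 mCi, so nominal group means agree. The pooled densities still mix two dose levels.
5. Tolerance as noise: if delivered activity is uniform within ±20% (assumption), its log-SD is 0.117. The standard error it adds to a difference in group log-means is 0.117 × √(2/3) = 0.096 with 3 per group and 0.117 × √(2/6) = 0.068 with 6. Unless it is related to group, it adds noise of about 7% to 10%, not bias.
6. Decay across an imaging window, 1 − 2^(−w/361.2 min): 1.9% for w = 10 min and 5.6% for w = 30 min. This is minor beside items 1 to 3.

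**Would a liver-to-spleen ratio be more sensitive?** No share below is in the documents. Let the liver start with share L and the spleen with S, let d be lost from the liver, and let a fraction f of d reach the spleen. The log-change multiple is ln{[(L−d)/(S+fd)]/(L/S)} / ln{(L−d)/L}. Ranges cover L/S = 80/10, 60/10 and 40/5 (% of activity) and d = 5, 10 and 20 percentage points.

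| f | Multiple of the liver-only log change |
|---|---|
| 0 | 1.0 |
| 0.1 | 1.45 to 1.76 |
| 0.2 | 1.83 to 2.48 |
| 0.5 | 2.58 to 4.46 |
| 1 | 3.32 to 7.28 |

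The mean shift in the ratio depends almost entirely on f. The ratio also carries spleen variance. As an illustration, take a 30% liver fall, 6 per group, liver log-SD 0.25, independent components and a two-sided 0.05 t-test (non-central t, 10 df, non-centrality |ln 0.7| / (s√(2/6))):

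| Measure | s | Power, f = 0 |
|---|---|---|
| Raw liver | √(0.25² + 0.117²) = 0.276 | 0.525 |
| Liver per injected activity | 0.25 | 0.61 |
| Ratio, spleen log-SD 0.05 | 0.255 | 0.59 |
| Ratio, spleen log-SD 0.20 | 0.320 | 0.41 |
| Ratio, spleen log-SD 0.30 | 0.391 | 0.30 |

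At f = 0 the ratio beats raw intensity only if spleen log-SD is below 0.117. At f = 0.1 its power is 0.72 to 0.80 (spleen log-SD 0.20) or 0.55 to 0.63 (0.30) across the three starting shares. The ranking can go either way on inputs the plan does not give.

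**The case against.** The case against giving the spleen any role is serious. The evidence of splenic uptake is from rats. The same study names urine as the main elimination route (mean 38.9% of dose) and ranks spleen concentration below urine, kidney, liver and bile. Tracer that the liver does not take up may therefore leave through the kidney, with f near zero. Splenic uptake or size may itself differ in F3-F4 disease and bias the ratio in either direction. Dividing by net injected activity separates uptake from dose without the spleen. The trial is a Phase 1 study with safety primary, liver-focused objectives and no formal tests.

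Most of this stands, and it rules out three stronger readings that a reader might infer:

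- That the liver-to-spleen ratio is the more sensitive or most robust index. The documents give no human splenic uptake, no spleen variability and no redistribution share.
- That reduced hepatic uptake can never be told from a smaller dose. It can, once net injected activity is measured and used; the plan states neither step.
- That the spleen data are discarded. Section 8.2 sends all images to the sponsor; they simply have no planned analysis.

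The objection does not remove the gap in sections 9.3 and 9.5.3. Section 9.5.3 defers detail to an SAP, but the document supplied contains no separate SAP text that closes it. Nor does normalisation make a within-scan reference redundant: partial extravasation and camera sensitivity across one to three centers are not removed by dividing by syringe activity, whereas they cancel in a ratio taken from one scan.

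**Conclusion.** The point holds for absolute liver uptake and intensity. As the analyses are stated, these are confounded with delivered activity: up to 1.5-fold between subjects on the same assignment, 3.2-fold between radiolabel levels, and 1.88-fold in group means under option 1 if all NASH subjects are pooled. The last figure is specific to option 1; under option 2 nominal group means agree. The dose factors follow from section 5.2 and assume that intensity scales with delivered activity. The noise figures assume a uniform spread within tolerance.

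The relative intrahepatic pattern is not affected by a common dose factor. No verdict is given on the voxel classes in section 9.5.3, because their threshold is not stated. The spleen enters only as a cheap additional within-scan reference. Its advantage over normalised liver intensity is unproven, and it can lose precision if redistribution is near zero.

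**What to change.** 1. In sections 5.5 and 8.2 and the CRF, record syringe activity before and after injection with assay and injection times, for both agents.
2. In sections 9.3 and 9.5.3, define liver intensity as decay-corrected intensity per net injected activity. Give summaries and densities by subject type within radiolabel level. Under option 1 the direct comparison is then three against three at 2.5 mCi, with the two 8.0 mCi NASH subjects shown separately.
3. In section 9.5.3, add as a descriptive exploratory output the liver-to-spleen ratio of mean SPECT intensity, with both organs outlined on the same-session CT, for each subject, agent and time point. Add the within-subject tilmanocept/sulfur colloid ratio of these ratios at 20 minutes, the one time point both agents share. Always show the separate liver and spleen values beside it, and make no claim of greater sensitivity.

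The cost is a residual-activity reading per injection, one extra organ outline on images already acquired, and a few lines of text. The downside is that splenic uptake or size may differ in F3-F4 disease, which is why the ratio must not stand alone. No dose, tolerance or review rule needs to change.
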